1.1 Literature Review

Chronic pancreatitis (CP) is a debilitating disease. Pain is the principal symptom associated with CP. The cause of pain may be multi-factorial. Correlation between morphological aspects of CP and phenotypical patient presentations including frequency and severity of pain is ill understood. Response to various treatment modalities for the pain – medical management, endotherapy, or surgery – is also poorly predicted. However, it is well recognized that in some patients the pancreatic type pain seems associated with pancreatic duct (PD) obstruction and associated PD dilation. Endotherapy using pancreatic stents may have a beneficial effect in such cases by calibrating the PD strictures, reducing upstream ductal dilation and reducing pain. However, calibration of PD strictures may not alleviate pain if the origin of the pain has causes other than PD hypertension and dilation. Thus, success of endotherapy using any type of PD stents should combine assessment of pain and calibration of the PD stricture without clinically significant stent-induced ductal changes.

In the treatment of benign PD strictures often in the presence of PD stones caused by CP, the ultimate clinical objective is acceptable quality of life including durable pain control without major complications, preferably stent-free. The gold standard of treatment in this indication remains surgery^{1,2}; however, the morbidity associated with these major surgical procedures has made endoscopic, less invasive alternatives a first-line approach for simple benign main PD strictures associated with CP at several expert centers. Endotherapy in this indication mostly consists of single or multiple pancreatic plastic stents²⁻¹¹. The most frequently quoted publication⁵ on long-term resolution of refractory PD strictures after temporary indwell of multiple plastic stents in patients with severe CP reports effectiveness comparable to surgical outcomes. A meta-analysis of publications of pancreatic plastic stenting in CP patients²⁻¹¹ was used as a basis to generate the hypothesis of the current trial.

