1.2 Prior Clinical Trials

In addition to the above publications, preliminary data is available from a small 10 patient trial conducted with the Fully Covered WallFlex Pancreatic Stent. Patients with painful chronic pancreatitis of Cremer Type IV were enrolled between June and September 2014. Intended indwell was 3 months in 5 patients and 6 months in 5 patients. In total 14 stents

August 28, 2017

Boston Scientific
WallFlex Pancreatic Pivotal Protocol
91067616 Rev/Ver AK
Page 17 of 64

were placed, with 2 patients having immediate removal and replacement of the initial stent due to deployment in unsatisfactory position and 2 patients needing a second stent placement after premature complete distal migration of the first indwelling stent. Stent migration without symptoms, thought to be a reflection of adequate calibration of the benign stricture, occurred in 6 stent placements, not requiring restenting. Clinically meaningful complete distal migration (CDM) with symptoms occurred in 25% (3/12) of stent placements with intended stent indwell. There were no proximal stent migrations. Endoscopic stent removal was performed per-protocol easily in one patient after a 3 month indwell and in 2 patients after a 6 month indwell without stent removal-related adverse events (AEs). After a median follow-up of 196 days (range 175 - 373) after stent removal or observation of CDM of the stent, 80% (8/10) of patients remained stent-free. Longer term follow-up is ongoing. One patient had premature CDM followed by placement of plastic stents. One patient had no pain relief after SEMS placement and had subsequent pancreatic diversion surgery which did not provide pain relief either. Serious Adverse events (SAEs) occurred in 50% (5/10) of patients, with 7 SAEs (2 pain associated with premature CDM, 2 transient pain related to stent expansion immediately following stent placement, 1 pain unresolved by stenting or subsequent pancreatic diversion surgery, 1 bacterial infection and 1 mild acute pancreatitis). No SEMS needed to be removed due to intolerable pain after SEMS placement. There were no stent-induced ductal changes.

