4.6 Restenting

Restenting with a non-study stent will take place if there is no improvement of clinical status (see definition in secondary endpoint 2) and associated persistence of the stricture based on imaging. Imaging will be conducted per standard of practice. Such may be prompted by lack of improved clinical status and may consist of non-invasive imaging or of a pancreatogram. A pancreatogram will only be performed if an ERCP is necessitated for a reintervention with or without restenting.

Restenting with a new study stent may only occur during the initial stent placement procedure for conditions such as stent misplacement, improper stent size choice, and other conditions, as necessary.

August 28, 2017

Boston Scientific
WallFlex Pancreatic Pivotal Protocol
91067616 Rev/Ver AK
Page 22 of 64

5 Patient Selection

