7.1 Data Collection

Procedure/Assessment	Screening/ Baseline	Study Stent Placement****	Month 1 (30 ± 5 Days)	Month 3 (90 ± 10 Days)	Month 6 Study Stent Removal (180 ± 15 Days)	Month 3 Post-Removal Follow-up Visit (90± 15 Days)	Month 6 Post-Removal Follow-Up Visit (180 days ± 15 days)
Informed consent form, including informed consent signature date	X						
Demographics and Medical and EPS History	X						
Weight*	X	X	X	X	X	X	X
EPS		X (if required)					
Pre-stenting pancreatic stone clearance (as applicable)	X***	X					
Study Stent Placement		X					
Study Stent Removal					X		
Pancreatic Duct Imaging (may be non-invasive)	X***	X Pre- and Post- Stent Placement			X** Post-Stent Removal		X
Pain Score, Average Daily Narcotic Dose, and QOL Score*	X	X (prior to all stent procedures)	X	X	X (prior to stent removal)	X	X
Adverse Event Assessment	X***	X	X	X	X	X	X
Concomitant Medications, including injectable narcotics	X	X	X	X	X	X	X

* Weight Pain Score and QOL must be assessed at all visits, including any unscheduled visits.

**Window for imaging is ±4 weeks.

***Applicable at Baseline visit for patients who undergo plastic stent placement for ESWL per inclusion criteria 9.

****Study Stent Placement visit may take place on the same day as Screening/Baseline, if deemed appropriate by the treating physician

Boston Scientific
WallFlex Pancreatic Pivotal Protocol
91067616 Rev/Ver AK
Page 27 of 64

August 28, 2017

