7.4 Scoring System

7.4.1 Izbicki Scoring System

The Izbicki Pain Scale incorporates four elements: 1) patient self-estimation of intensity of pain using a visual analog scale (VAS), 2) the frequency of pain attacks, 3) analgesic medication usage and 4) the time periods of inability to work. The sum of the rank values divided by four gives the final value of the pain score. See Appendix 22.1 for the Pain Scale.

Patients will be asked to report on the average pain experienced since the prior visit when reporting pain via VAS for the first element of the Izbicki Pain Scale. Patients will be asked to report the average frequency of pain attacks experienced since the prior visit for the second element of the Izbicki Pain Scale. Please see Appendix 22.5 for further guidance on collecting the VAS and frequency of pain attacks information.

Note: For centers with medication types that do not align with section 3 of the Izbicki Pain scale, relevant corresponding medication types may be made available for scoring.

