8.1 Endpoints

8.1.1 Primary Endpoint

Primary Effectiveness Endpoint:

Pain Reduction

Pain reduction will be assessed at 6 months post-stent removal or 6 months post-observation of complete or partial stent migration compared to pain collected at baseline. Baseline for patients without a plastic pancreatic stent immediately prior to study stent placement will be at the time of enrollment. Baseline for patients with a plastic pancreatic stent immediately prior to study stent placement will be at the time of study stent placement.

Pain will be scored between 0 and 100 as the mean of the VAS Pain Score and Frequency of Pain sectors of the Izbicki pain scale.

Complete pain relief is defined as pain score ≤ 10 , and partial pain relief is defined as pain score > 10 and reduced by at least 50% compared to baseline.

Complete or partial pain relief in the setting of a 50% higher average daily narcotic dose will be considered a primary effectiveness endpoint failure. Average daily narcotic dosage for prior month will be assessed at baseline visit prior to plastic or study stent placement, whichever is implanted first, and at 6 months post-stent removal/observation of complete distal migration.

Patients who experience stent migration in setting of recurring pain (VAS Pain Score of ≥ 20) will be considered as having failed the primary effectiveness endpoint.

Patients who are restented in the setting of recurring pain will be considered as having failed both the primary effectiveness endpoint and the secondary stricture resolution endpoint and may only be restented with a non-study stent.

Restenting with a new study stent may only occur during the initial stent placement procedure for such situations as stent misplacement, improper stent size choice, or other conditions, as necessary and will not be considered a primary effectiveness endpoint failure or a secondary effectiveness stricture resolution endpoint failure.

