22.5 Guidance on Collecting VAS Pain Score and Frequency of Pain Attacks Information

The Izbicki Pain Scale incorporates the following four elements in its measurement of pain:

- 1) patient self-estimation of intensity of pain using a visual analog scale (VAS)
- 2) the frequency of pain attacks
- 3) analgesic medication usage
- 4) the time of disease-related inability to work

The sum of the rank values divided by four gives the final value of the pain score. Please see Appendix 22.1 for more information. The Izbicki Pain Scale will be collected at every study visit. The information below will serve as guidance when collecting information for the first two elements of the Izbicki Pain Scale.

When reporting pain via VAS for the first element of the Izbicki Pain Scale, patients will be asked to report on the average pain experienced since the prior study visit. For the second element of the Izbicki Pain Scale, patients will be asked to report the average frequency of pain attacks experienced since the prior study visit. The manner in which these two questions are posed will depend upon the patient's pain pattern.

What is the patient's pain pattern?

Short and relapsing episodes of pain separated by periods of pain remission	Prolonged periods of fairly constant pain	Unknown or indistinguishable pattern of pain

1st Study Visit Within the previous three months, how strong was your most severe bout of pain? & Within the previous three months, how frequently did you experience a bout of pain?
 
Follow-up Study Visit Since the last study visit, how strong was your most severe bout of pain? & Since the last study visit, how frequently did you experience a bout of pain?
	
1st Study Visit Within the previous three months, how would you score the average level of pain you experienced? & Within the previous three months, how frequently have prolonged periods of pain occurred?
 
Follow-up Study Visit Since the last study visit, how would you score the average level of pain you experienced? & Since the last study visit, how frequently did prolonged periods of pain occur?
	
1st Study Visit Within the previous three months, how would you score your pain? & Within the previous three months, how frequently have you experienced pain?
 
Follow-up Study Visit Since the last study visit, how would you score your pain? & Since the last study visit, how frequently have you experienced pain?

August 28, 2017

Boston Scientific

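### Restenting for recurring pain is scored as failure but pancreatic surgery for pain is not, so relief from an operation can count as stent success

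*Combined protocol and SAP*

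**What the plan says.** Success is a pain score of 10 or less, or a fall of at least half from baseline, at 6 months after stent removal or observed migration. The synopsis, section 4.1 and section 8.1.1 override that result to failure in three cases:

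- an average daily narcotic dose 50% higher than at baseline;
- stent migration with recurring pain (VAS of 20 or more);
- restenting: "Patients who are restented in the setting of recurring pain will be considered as having failed both the primary effectiveness endpoint".

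Surgery is not on the list. It is also absent from the withdrawal reasons (6.3), study completion (7.12) and the missing-data rules (8.1.2, 8.1.3).

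The protocol does foresee surgery. Section 1.1 states: "The gold standard of treatment in this indication remains surgery". Section 1.2 reports that one of the ten pilot patients had no relief from the stent and "had subsequent pancreatic diversion surgery which did not provide pain relief either".

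**The concern.** Restenting and surgery are both rescue treatments for a stent that did not control pain. The plan scores the first as failure and leaves the second to whatever pain score is observed. This is a single-arm test against a fixed 53% goal, so there is no control group in which the same credit would cancel out. Any relief obtained by an operation goes straight into the stent's success count.

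The restenting rule does not catch every such patient. Section 4.6 ties restenting to lack of clinical improvement "and associated persistence of the stricture based on imaging". A patient whose stricture has opened but who still has pain does not meet that condition, and section 1.1 accepts that this happens: "calibration of PD strictures may not alleviate pain if the origin of the pain has causes other than PD hypertension and dilation". The missing-data rules do not help either, because the 6-month score of an operated patient who stays in follow-up is observed.

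**Working it through.** **1. The plan's own figures.** Inputs from 8.1.2 and the synopsis: goal 53%, assumed rate 75%, exact test, one-sided 0.025, power 80%.

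- n = 43: reject at 30 or more successes. P(Bin(43, 0.53) ≥ 30) = 0.0190; P(Bin(43, 0.75) ≥ 30) = 0.834. At n = 42 the rule is again 30 and power is 0.766. The stated 43 reproduces.
- Final size: 57/0.90 = 63.3, so 64, as stated.

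**2. Decision rules at the planned sizes.**

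- n = 64: P(X ≥ 43) = 0.0150 and P(X ≥ 42) = 0.0280, so 43 successes are needed.
- n = 57 (after the 10% loss): P(X ≥ 39) = 0.0131 and P(X ≥ 38) = 0.0256, so 39 are needed.

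**3. Effect of the gap.** Let k patients be stent failures who are relieved by surgery and counted as successes. Hold the overall stent success rate at 53%, so the other n − k patients succeed with probability 0.53n/(n − k). With c the number of successes required, the chance of passing is P(Bin(n − k, 0.53n/(n − k)) ≥ c − k). For n = 64 and k = 1 the probability is 33.92/63 = 0.538, and P(Bin(63, 0.538) ≥ 42) = 0.0267.

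| k (assumed) | n = 64, c = 43 | n = 57, c = 39 |
|---|---|---|
| 0 | 1.5% | 1.3% |
| 1 | 2.7% | 2.4% |
| 2 | 4.5% | 4.3% |
| 3 | 7.4% | 7.2% |
| 5 | 17.3% | 17.8% |

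The nominal 2.5% is passed at k = 1 for n = 64, and at k = 2 for n = 57. Under the null about 0.47 × 64 = 30 patients are stent failures, so k = 1 is about 1/30 = 3.3% of them.

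As a cross-check, add a share s of surgery-relieved patients to the 53%. At n = 64, s = 2% gives P(Bin(64, 0.55) ≥ 43) = 3.2%, and s = 5% gives 8.5%.

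**4. What the documents say about k.** In the pilot 1 of 10 patients was operated on (exact 95% CI 0.3% to 44.5%), and 0 of 1 was relieved. This does not fix k, so the table is a sensitivity range and not a forecast.

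**5. Which operations are exposed.** Section 7.4.1 says: "Patients will be asked to report on the average pain experienced since the prior visit when reporting pain via VAS". For relapsing pain, section 22.5 asks instead: "Since the last study visit, how strong was your most severe bout of pain". Either way, surgery after the 3-month post-removal visit generally leaves some pre-operative pain in the 6-month score. The gap therefore mainly concerns surgery before that visit. With removal at day 180 and visits on schedule, that means up to day 270 of 360, or 270/360 = 75% of follow-up. An additional visit after a later operation restarts the recall window, since "Pain Score and QOL must be assessed at all visits, including any unscheduled visits" (7.1).

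**The case against.** The strongest case against is that the route is narrow. The patient must have surgery, be relieved by it, stay in the study, have a recall window clear of pre-operative pain, and meet none of the three failure rules. Symptomatic complete distal migration, which occurred in 3 of 12 pilot placements, would usually lead to failure under the migration rule. The only operated pilot patient was not relieved and would have failed under the present wording. No document supports any particular k of 1 or more, and k = 1 barely matters: 2.67% at n = 64 and 2.42% at n = 57. The 75% window is a share of calendar time, not of risk, and does not apply if surgery came with early stent removal. All of this stands, and it limits the expected size of the problem. It does not supply the missing scoring rule.

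Two further points also have weight. The documents do not show how the ten publications behind the 53% goal scored relief after surgery; if they counted it as success, scoring it as failure makes the test stricter than its benchmark. And reintervention without restenting, which 4.3 and 4.6 foresee, is equally unscored. The first is a reason for the sensitivity analysis. The second is a reason to widen the rule, not to leave surgery out.

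Safety reporting covers part of the ground, since a related serious event would count in the safety endpoint. That does not alter the effectiveness score.

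**Conclusion.** The concern holds. Applied as written, the endpoint credits the stent with relief obtained by surgery, although the parallel rescue by restenting is already a failure. The stated sample sizes are correct; the fault is in the endpoint definition.

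The size depends on an assumed number of surgery-relieved patients. One at n = 64, or two at n = 57, takes the false-positive rate above 2.5%; three takes it to about 7% at either size. This rests on a true stent success rate of exactly 53% and on operated patients meeting no other failure rule. Confidence is medium, because the frequency of such patients, their relief rate and the scoring used in the literature are all unknown from the documents. The point should be corrected, but it does not invalidate the design.

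**What to change.** Add one sentence, identical in the synopsis, 4.1 and 8.1.1: *Pancreatic surgery for pain at any time from study stent placement to the 6-month post-removal or post-migration assessment counts as failure of the primary effectiveness endpoint, whatever pain score is observed.* The same sentence can usefully say how reintervention for pain without restenting is scored.

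Record the date, type and reason of any such surgery as a separate item. Section 16.1 does not collect unrelated adverse events, so surgery judged unrelated to the stent might otherwise not be recorded systematically. Report a sensitivity analysis that uses the observed score regardless of surgery. It shows the result both ways, given that the scoring behind the 53% goal is unknown.

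The rule concerns scoring only and does not touch care. The cost is one sentence in three places, one recorded item and one analysis, with no extra patients or visits.

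The downside is a possibly lower observed success rate. If the assumed 75% had included k surgery-relieved patients, power would be P(Bin(n − k, (0.75n − k)/(n − k)) ≥ c). For k = 0, 1, 2 this is 94%, 90%, 85% at n = 64 and 90%, 84%, 76% at n = 57. That premise is cautious: 8.1.2 derives the 75% from 8 of 10 pilot patients staying stent-free, and 1.2 describes the operated patient separately from those eight.

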Primary Statistical Hypotheses	
A literature search was performed on plastic pancreatic stenting in CP. Ten (10) articles that represent 392 evaluable patients²⁻¹¹ were found.
 
Primary Effectiveness Endpoint:
 
A meta-analysis of “pain reduction” reported in these articles yielded a point estimate of 66% with a 95% Confidence Interval (CI) of 53% to 76%, using a random effects model.
 
Statistical testing will be conducted to determine if “pain reduction” using the WallFlex Pancreatic Stent is greater than 53%, assuming an observed “pain reduction” rate of 75% and using an exact test with a one-sided alpha of 0.025 and power of 80%, 43 patients will be required.
 
Primary Safety Endpoint:
 
The same literature search as above was used; however, one article, Seza et al. did not report on “related serious adverse events.” Therefore, nine (9) articles representing 386 evaluable patients were found. A meta-analysis of “related serious adverse events” reported in these articles yielded a point estimate of 25% with a 95% CI of 19% to 32%, using a random effects model.
 
Statistical testing will be conducted to determine if “related serious adverse events” is less than 32%, assuming an observed “related serious adverse event” rate of 15% and using an exact test with a one-sided alpha of 0.025 and power of 80%, 57 patients will be required.
 
Taking the larger of the two hypotheses and compensating for possible loss of patients after enrollment, an additional 10% of patients will be required, for a total of 64 patients.
 
The percentage of patients who do not meet the inclusion criteria levels of the VAS pain score (≥ 20) and frequency of pain score (50, 75, or 100) at the time of study stent placement, due to a prior single plastic pancreatic stent, is anticipated to range from 20-30%. Therefore, we propose to enroll up to 92 patients so as to have 64 patients who met the inclusion criteria levels of the VAS pain score (≥ 20) and frequency of pain score (50, 75, or 100) at the time of study stent placement.

---------------------------------------	--

August 28, 2017

Boston Scientific
 WallFlex Pancreatic Pivotal Protocol
 91067616 Rev/Ver AK
 Page 10 of 64

Table of Contents

1	Introduction	15
1.1	Literature Review.....	15
1.2	Prior Clinical Trials.....	17
1.3	Conclusion	18
2	Device Use and Description	18
2.1	Device Description.....	18
2.2	Device Use	19
3	Primary Objective	19

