Use of self-expanding metal stents (SEMS) in benign main PD strictures associated with painful chronic pancreatitis (CP) was first described in the 1990s, culminating in a recommendation¹² that use of uncovered SEMSs in the PD should be avoided and that use of covered SEMSs (CSEMSs) in the PD holds promise in this indication. Compared to resective or bypass surgery, the use of SEMS is less invasive. Compared to MPS, the use of SEMS is anticipated to result in similar long-term stent-free pain relief, however requiring a shorter duration of stent therapy and fewer ERCPs. Literature-based values are summarized below.

August 28, 2017

Boston Scientific
WallFlex Pancreatic Pivotal Protocol
91067616 Rev/Ver AK
Page 15 of 64

Table 1.1-1: Plastic Stent Literature Values

Study	Number of ERCPs	Total PS indwell duration
Eleftheriadis 2005 ²	Median 3 Range 1-18	Median 23 months Range 2-134 months
Vitale 2004 ³	Mean 4.1	Range 3-12 months
Topazian 2005 ⁴	Mean 3.2	Intended 6 months, actual duration not reported
Costamagna 2006 ⁵	Not reported	Mean 7 months Range 5-11 months
Farnbacher 2006 ⁶	Not reported	Mean 10 months±10 months
Ishiara 2006 ⁷	Not reported	Mean 335±31 days
Cahen 2007 ⁸	Median 5 Range 1-11	Mean 27 weeks Range 6-67
Weber 2007 ⁹	Not reported	Mean 5.6 months Range 1-1- months
Seza 2011 ¹⁰	Not reported	Mean 15.2±3.1 months
Gabrielli 2005 ¹¹	Not reported	Not reported

A literature review of 2000-2012 yielded 5 publications with series of 5 or more cases totaling 72 cases¹³⁻¹⁷ pertaining to benign PD stricture resolution after treatment using CSEMS. After stent indwell ranging from 2 to 9 months, CSEMS removal was attempted in 71 patients and was achieved without difficulty in 97% (69/71). In 3% (2/71) CSEMS were embedded and required a stent-in-stent technique for subsequent removal. Overall clinical success after post stent removal follow-up ranging from 4 to 20 months averaged 83% (59/71) (range 40%-100%). The overall reintervention rate was 18% (13/72) (range 8%-45%). There were 22 reported stent-related complications in 72 patients, including immediate post FCSEMS placement pain that may require stent removal in some patients.

Of note are publications by the American Society of Gastroenterological Endoscopy (ASGE) and the European Society of Gastroenterological Endoscopy (ESGE) on endotherapy in patients with painful CP:

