4.3 Secondary Endpoints

Effectiveness

1. Stricture Resolution

Stricture resolution will be assessed at the time of stent removal or observation of complete or partial stent migration.

Stricture resolution is defined as maintained pain relief without need for restenting or, if pain recurs, confirmation of stent patency adequate for providing drainage of the pancreatic duct.

Restenting with a non-study stent will take place if there is no improvement of clinical status (see definition in secondary endpoint 2 below) and associated persistence of the

August 28, 2017

Boston Scientific
WallFlex Pancreatic Pivotal Protocol
91067616 Rev/Ver AK
Page 20 of 64

stricture based on imaging. Imaging will be conducted per standard of practice and may be prompted by lack of improved clinical status and may consist of non-invasive imaging or pancreatogram. A pancreatogram will only be performed if an ERCP is necessitated for a reintervention with or without restenting.

NOTE: Patients who are restented for recurring pain (VAS Pain Score of ≥ 20) will be considered a failure for stricture resolution and the primary endpoint and may only be restented with a non-study stent.

Restenting with a new study stent may only occur during the initial stent placement procedure for such situations as stent misplacement, improper stent size choice, or other conditions, as necessary and will not be considered a secondary effectiveness stricture resolution endpoint failure or a primary effectiveness endpoint failure.

2. Improved clinical status compared to baseline assessed at each study visit.

Improved clinical status is defined as improvement in at least one and deterioration in none of the following: Pain, Weight and Quality of Life (QOL)

- *Pain: Scored between 0 and 100 as the mean of the VAS Pain Score and Frequency of Pain sectors of the Izbicki pain scale.*
- *Weight is measured*
- *Quality of life: Recorded using SF12*

3. Recurrence of Stricture documented by recurrence of pain with loss of adequate pancreatic duct drainage.

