8.1.2 Hypotheses/Sample Size

Ten (10) articles²⁻¹¹ were identified to be reporting on “pain reduction,” representing 392 evaluable patients. One of these articles¹⁰ did not report on “related SAE rate”; thus, for this endpoint we used 9 articles^{2-9,11}, representing 386 evaluable patients. The table below provides by-publication “pain reduction” and “related SAE” rate used to conduct respective meta-analyses.

Meta-analyses were conducted using a random effects model. The sample sizes were calculated using SAS version 9.4.

Table 8.1.2-1: Pain Reduction and Related SAE Rates by Publication

Study	“Pain Reduction”	“Related SAEs”
Eleftheriadis 2005 ²	62% (62/100)	25% (25/100)
Vitale 2004 ³	83% (62/75)	19% (17/89)
Topazian 2005 ⁴	60% (9/15)	47% (7/15)
Costamagna 2006 ⁵	84% (16/19)	0% (0/19)
Farnbacher 2006 ⁶	55% (53/96)	28% (27/96)
Ishiara 2006 ⁷	78% (7/9)	0% (0/9)
Cahen 2007 ⁸	32% (6/19)	26% (5/19)
Weber 2007 ⁹	82% (14/17)	12% (2/17)
Seza 2011 ¹⁰	85% (17/20)	N/A
Gabrielli 2005 ¹¹	32% (7/22)	32% (7/22)

August 28, 2017

Boston Scientific
WallFlex Pancreatic Pivotal Protocol
91067616 Rev/Ver AK
Page 33 of 64

Pain reduction

For “pain reduction” the meta-analysis yielded a point estimate of 66% with a 95% Confidence Interval (CI) from 53% to 76%.

Statistical testing will be performed to determine if the probability of “pain reduction” when using the WallFlex Pancreatic Stent is greater than the performance goal (PG) set at 53%, the lower bound of the 95% CI from the meta-analysis above. Hence, the following hypothesis will be tested:

$$H_0: \pi_1 \leq 53\%$$

$$H_a: \pi_1 > 53\%$$

where π_1 is the probability of observing “pain reduction”.

Assuming that the observed probability is 75%, 43 patients will be required for the above hypothesis, with a one-sided alpha of 0.025 and power of 80%.

The observed probability of pain reduction was set to 75% given that 8 out of 10 patients in a 10 patient pilot study remained stent free at 6 months post-removal. The primary effectiveness endpoint will be assessed in two ways, namely one using last observation carried forward for patients that are missing 6 month pain data and one counting patients with 6 month pain data as failures. A tipping point analysis will be performed to assess the validity of the associated conclusions.

Related SAEs

For “related SAE rate” the meta-analysis yielded a point estimate of 25% with a 95% CI from 19% to 32%.

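### A patient given a non-study stent for a persistent stricture, without recurring pain, can still count as a primary effectiveness success of the study stent

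*Combined protocol and SAP*

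**What the plan says.** **Failure rule.** The synopsis, Section 4.1 and Section 8.1.1 carry the same sentence on later restenting: "Patients who are restented in the setting of recurring pain will be considered as having failed both the primary effectiveness endpoint". It gives no pain threshold. A note to the stricture-resolution endpoint in Section 4.3 (also in the synopsis) does give one when it names as failures "Patients who are restented for recurring pain (VAS Pain Score of ≥ 20").

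**Restenting rule.** Section 4.6, like Section 4.3 item 1, states: "Restenting with a non-study stent will take place if there is no improvement of clinical status". It adds a second condition, that the stricture persists on imaging. Section 4.3 item 2 sets the clinical-status test: "Improved clinical status is defined as improvement in at least one and deterioration in none of the following". The components are pain, weight and SF-12 quality of life, so worsening in any one of them means that status has not improved. Section 4.3 item 3 has a separate route for recurrence: clinical status deteriorates and imaging documents a recurrent stricture.

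**Assessment.** The primary pain score is taken 6 months after study-stent removal or observed migration. Success is a score of 10 or less, or a reduction of at least half from baseline. Under Section 7.12, follow-up runs from the initial stent removal or from observed complete distal migration. No text takes a restented patient out of the 6-month assessment.

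**The concern.** The grounds for placing a non-study stent are wider than the grounds for calling restenting a primary failure. A patient who falls between the two has the 6-month pain score taken with, or after, another device, and that score can be credited to the study stent. In a single-arm trial tested against a fixed goal, no control group offsets this. Compared with scoring such patients as failures, the gap can only move them from failure to success.

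The endpoint is also looser on restenting than the evidence used to power it. Section 8.1.2 bases the assumed 75% on 8 of 10 pilot patients who were stent-free 6 months after removal. By that standard a patient carrying a later stent is not a success.

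**Working it through.** **1. Which restented patients escape the failure rule?**

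| Situation leading to a non-study stent | Restenting called for? | Primary failure by the restenting sentence? |
|---|---|---|
| Pain improved, weight or SF-12 worse, stricture persists on imaging | Yes (4.3 item 1, 4.6) | No: no pain has recurred |
| Pain never relieved, stricture persists | Yes | Unclear: literally it persists and does not recur; if recurring simply means VAS ≥ 20, it fails |
| Frequent pain with VAS below 20, clinical status not improved, stricture persists | Yes | Unclear: the primary sentence has no threshold; the Section 4.3 note uses VAS ≥ 20 |
| Clinical status worse, stricture recurs | Yes (4.3 item 3) | Mostly yes: the endpoint is defined by recurrence of pain |
| Weight loss or poor SF-12 alone, no stricture on imaging | No | Does not arise |

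The first row is the clear gap. As an example of the third row, daily pain (100 points) with VAS 15 gives a pain score of (100 + 15)/2 = 57.5, although VAS is below 20.

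**2. Does another rule close the gap?** The other primary failure rules cover a 50% higher narcotic dose and migration with VAS ≥ 20. Neither addresses the first row. Restenting does count in stricture resolution, stricture recurrence and stent functionality, but these are secondary endpoints.

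**3. The plan's own sample size.** Inputs from the synopsis and Section 8.1.2: the rate must be "greater than the performance goal (PG) set at 53%, the lower bound of the 95% CI from the meta-analysis above"; "Assuming that the observed probability is 75%, 43 patients will be required for the above hypothesis"; the synopsis specifies "using an exact test with a one-sided alpha of 0.025 and power of 80%, 43 patients will be required".

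For n patients the pass mark r is the smallest integer with P(X ≥ r | n, 0.53) ≤ 0.025, and power is P(X ≥ r | n, 0.75).
- n = 43: r = 30, size 0.0190, power 0.834.
- n = 42: r = 30, power 0.766.
- Power stays at or above 80% for every n checked from 43 to 49.

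The stated 43 reproduces.

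**4. Sensitivity at the margin.** Section 8.1.2 aims for 64 patients who meet the pain criteria at study stent placement. If all 64 are evaluable, p = P(X ≥ x | 64, 0.53):
- 43/64: 0.0150, passes.
- 42/64: 0.0280, does not pass.
- 41/64: 0.0488.

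One patient rescored from success to failure at the pass mark reverses the conclusion. The same holds with 57 evaluable: 39/57 gives 0.0131 and 38/57 gives 0.0256. At the planned rate, 0.75 × 64 = 48 successes, six rescored patients are needed to lose significance (42/64).

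**5. Illustrative effect on passing.** Suppose the success rate without the gap is 53%, and the gap adds m points. The size of m is an assumption. With n = 64 the pass probability is P(X ≥ 43 | 64, 0.53 + m):

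| m (points) | Patients of 64 | Pass probability |
|---|---|---|
| 0 | 0 | 1.5% |
| 1 | 0.01 × 64 = 0.6 | 2.2% |
| 3 | 0.03 × 64 = 1.9 | 4.5% |
| 6 | 0.06 × 64 = 3.8 | 11.3% |

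**The case against.** **The gap is narrow.** A reader might infer that restenting for unrelieved pain, weight loss or poor quality of life generally escapes the failure rule. The documents do not support that. Every route also needs a stricture on imaging. The recurrence route is framed by recurrence of pain and so is mostly caught. Unrelieved pain and frequent low-intensity pain both escape only if the rule requires pain that has returned and also VAS ≥ 20. The primary sentence does not state the threshold, and the note says who fails without saying that everyone else passes. These points stand, and they leave one clear case and two ambiguous ones.

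**The test may keep its size.** The hypothesis concerns the probability of pain reduction as the plan defines it, and for that parameter the size at n = 64 is 1.5%. Section 1.1 does say "the use of SEMS is anticipated to result in similar long-term stent-free pain relief", but as an expectation in comparison with multiple plastic stents, not as the reason for the endpoint's timing. So the 4.5% and 11.3% are errors against a stricter reading of success, not against the hypothesis as written. This also stands. What remains is the question of what a positive result could be said to show about the study stent.

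**The size is unknown.** It is tempting to take a share of the 18% (13/72) reintervention rate in Section 1.1. That figure covers all reinterventions over 4 to 20 months, the protocol itself separates reintervention with and without restenting, and any share falling outside the failure rule would be invented. In the clear case, pain may already have been low before the second stent, so that stent need not have created the success. At 1 added point the pass probability is still below 2.5%.

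**The goal comes from series with repeated procedures.** Table 1.1-1 shows repeated ERCPs in several of the plastic-stent series, and the documents do not say whether those series counted restenting as failure. A very strict rule might reduce comparability. This argues for limiting the fix to stricture-related restenting.

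**Conclusion.** The gap is real and should be fixed, but it is narrow. The texts of Sections 4.3, 4.6 and 8.1.1 together allow a patient restented for a persistent stricture, with improved pain and worse weight or SF-12, to be scored as a study-stent success. For never-relieved pain, and for frequent pain with VAS below 20, the plan leaves the classification to the reader. Restenting for recurrence is mostly covered already.

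The direction is certain relative to counting these patients as failures: the observed rate can only rise. The size is not known. The 1, 3 and 6 points are assumptions, and the calculation takes all 64 patients as evaluable. The effect matters near the pass mark, where one patient is enough. It matters little if the result is close to the planned 75%. The sample-size calculation itself is sound.

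**What to change.** In the synopsis, Section 4.1 and Section 8.1.1, replace the sentence on later restenting with a counting rule such as: *Any placement of a non-study pancreatic duct stent for a persistent or recurrent stricture, after the initial study stent placement procedure and before the 6-month primary assessment, is a primary effectiveness failure, whether or not pain has recurred.* Keep the exemption for exchanging a study stent during the initial procedure, and keep the existing failure of the stricture-resolution endpoint.

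Wording that failed a patient for a later stent placed for any reason would go beyond the gap, since it would also catch stents placed for reasons other than the stricture.

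The rule changes only how patients are counted; when to restent is untouched. It uses data already collected, settles the two ambiguous cases without a judgement after the fact, and leaves 43, 64 and 92 unchanged. The cost is a slightly lower observed success rate.
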